7.1 Treatments Administered

The study treatment(s) to be used in this trial are outlined below in Table 4.

	I		ose Escalation Phase ^a	I		
Study Treatment	Dosage	Dose Unit	Regimen/ Treatment	Dose	Route of Adminis-	
Name	Formulation	Strength	Period	Frequency	tration	Sourcing
MK-1308	Solution for	25 mg	Escalation/ Day 1 of	Q3W		Provided
	infusion	100 mg/	each cycle \times 5 doses.		H I · C ·	centrally by
		2 mL vial		0.0111	IV infusion	Sponsor
	Solution for	75 mg	Escalation/Day 1 of	Q3W		
	infusion	100 mg/	each cycle \times 5 doses.			
	Solution for	2 mL vial		0211/	-	
	solution for infusion	200 mg 100 mg/	Escalation/Day 1 of each cycle \times 5 doses.	Q3W		
	infusion	2 mL	each cycle × 5 doses.			
		vial				
Pembrolizumab	Solution for	200 mg	Escalation/Day 1 of	Q3W	IV infusion	-
(MK-3475)	infusion	100 mg/	each cycle starting at	Q3 W	i v infusion	
(10111-3473)	musion	4 mL vial	Cycle 2 ^a			
			e Confirmation Phase ^a			
Study		Dose			Route of	
Treatment	Dosage	Unit	Regimen/ Treatment	Dose	Adminis-	
Name	Formulation	Strength	Period	Frequency	tration	Sourcing
MK-1308	Solution for	25 mg	Confirmation/Arm A-	Q3W		Provided
	infusion	U	Day 1 of each cycle		IV infusion	centrally by
		100 mg/	Confirmation/ Arm B-	Q6W		Sponsor
		2 mL vial	Day 1 of every other	-		_
			cycle			
	Solution for	75 mg	Confirmation/Arms C	Q6W		
	infusion		and D- Day 1 of every		IV infusion	
			other cycle			
		100 mg/	Confirmation/Arm E-	Q3W		
		2 mL vial	Day 1 of each cycle			
Pembrolizumab	Solution for	200 mg	Confirmation/ Day 1 of	Q3W	IV infusion	
(MK-3475)	infusion	100 mg/	each cycle starting at			
		4 mL vial	Cycle 1 ^a			
 			cacy Expansion Phase ^b			1
Study Treatment	Dosage	Dose Unit	Regimen/ Treatment	Dose	Route of Adminis-	
Name	Formulation	Strength	Period	Frequency	tration	Sourcing
ivanic	Formulation	25 mg	I CI IOU	Trequency	tration	Sourcing
		MK-1308				
		+				
NUZ 1200 -		400 mg				D 111
MK-1308 +		pembro	Efficacy expansion			Provided centrally by
pembro Co-	Solution for	25 mg /	phase/	Q6W	IV infusion	Sponsor
administration	infusion	0.5 mL vial	Arm F- Day 1 of every	QOW	I V IIIIusioii	Sponsor
admixture		MK-1308	cycle, Option 1			
dumixture		+				
		100 mg/				
		4 mL vial				
		pembro				
		25 mg MK-				
		1308	Efficacy expansion			
MIZ 1209	Solution for	100 /	- phase/	OGW.	IV infusion	
MK-1308	infusion	100 mg/	Arm G - Day 1 of every	Q6W	1 v infusion	
		2 mL vial	other cycle			
		or 25 mg/				
		0.5 mL vial				
		U.J ML VIAI	1		1	

Coformulation Phase ^c						
Study Treatment Name	Dosage Formulation	Dose Unit Strength	Regimen/ Treatment Period	Dose Frequency	Route of Adminis- tration	Sourcing
MK-1308A	Solution for infusion	25 mg MK-1308 + 400 mg pembro 25 mg MK- 1308 + 400 mg pembro/ 17.5 mL vial	Coformulation Phase (Arms I, K)	Q6W	IV infusion	Provided centrally by Sponsor
Pembrolizumab (MK-3475) ^d	Solution for infusion	200 mg 400 mg 100 mg/ 4 mLvial	Coformulation Phase (Arm I)	Q3W Q6W	IV infusion	Provided centrally by Sponsor

IV = intravenous; pembro = pembrolizumab; Q3W = every 3 weeks; Q6W = every 6 weeks.

a For dose escalation and dose confirmation, pembrolizumab will be administered as an IV infusion over 30 minutes. MK-1308 will be administered as an IV infusion over 30 minutes. MK-1308 will be administered 30 minutes after completion of pembrolizumab infusion on the days when pembrolizumab is administered. In the dose escalation phase of the study, pembrolizumab administration will start in Cycle 2 and in the dose confirmation phase pembrolizumab administration to the dose levels detailed in this table, intermediate doses may also be evaluated in consultation and agreement with the investigators and Sponsor.

b For the efficacy expansion phase, Arm F pembrolizumab and MK-1308 will be co-administered in the same infusion bag over 30 minutes. For Arm G, MK-1308 will be administered alone. Participants in Arm F or G who cross over will receive the doses of MK-1308 and MK-3475 as determined by interim analysis at the time of crossover.

c For the coformulation phase, the solution will be infused over 30 minutes.

d In cases where toxicity is attributed to MK-1308A, participants may be re-initiated with pembrolizumab monotherapy at either 200 mg Q3W or 400 mg Q6W, after communication and agreement with the Sponsor.

All supplies indicated in Table 4 will be provided per the 'Sourcing' row depending upon local country operational requirements. Every attempt should be made to source these supplies from a single lot/batch number. The trial site is responsible for recording the lot number, manufacturer, and expiry date for any locally purchased product as per local guidelines unless otherwise instructed by the Sponsor.

Refer to section 9.1.8 for details regarding administration of the study treatment.

7.1.1 Definition of Dose-limiting Toxicity

All toxicities will be graded using NCI CTCAE Version 4.03 based on the investigator assessment.

The DLT window of observation will encompass the first 2 cycles of treatment for dose escalation and the first 1 cycle for dose confirmation, efficacy expansion, and coformulation (Arm I only).

The occurrence of any of the following toxicities during the DLT window will be considered a DLT, if assessed by the investigator to be possibly, probably or definitely related to study drug administration, excluding toxicities clearly not related to the drug, such as disease progression, environmental factors, unrelated trauma, etc.:

- 1. Grade 4 non-hematologic toxicity (not laboratory).
- 2. Grade 4 hematologic toxicity lasting \geq 7 days, except thrombocytopenia:
 - Grade 4 thrombocytopenia of any duration
 - Grade 3 thrombocytopenia associated with bleeding that requires a platelet transfusion
- 3. Any non-hematologic AE ≥Grade 3 in severity should be considered a DLT, with the following exceptions: Grade 3 fatigue lasting ≤ 3 days; Grade 3 diarrhea, nausea, or vomiting without use of anti-emetics or anti-diarrheals per standard of care; Grade 3 rash without use of corticosteroids or anti-inflammatory agents per standard of care.
- 4. Any Grade 3 or Grade 4 non-hematologic laboratory value if:
 - Clinically significant medical intervention is required to treat the participant, or
 - The abnormality leads to hospitalization, or
 - The abnormality persists for >1 week.
 - The abnormality results in a drug-induced liver injury (DILI) (see Section 9.3.7 for criteria)
- 5. Febrile neutropenia Grade 3 or Grade 4:
 - Grade 3 is defined as absolute neutrophil count ANC <1000/mm³ with a single temperature of >38.3° C (101° F) or a sustained temperature of ≥38° C (100.4° F) for more than one hour
 - Grade 4 is defined as ANC <1000/mm³ with a single temperature of >38.3° C (101° F) or a sustained temperature of ≥38° C (100.4° F) for more than one hour, with life-threatening consequences and urgent intervention indicated.
- 6. Prolonged delay (>2 weeks) in initiating Cycle 2 or Cycle 3 in Dose Escalation due to treatment-related toxicity; Prolonged delay (>2 weeks) in initiating Cycle 2 in Dose Confirmation due to treatment-related toxicity.
- 7. Any treatment-related toxicity that causes the participant to discontinue treatment during the DLT observation period.
- 8. Grade 5 toxicity.

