6.5 Participant Replacement Strategy

Participants discontinuing within the DLT window due to reasons unrelated to study treatment will not be considered evaluable for DLTs and may be replaced. Participants with a DLT within the DLT window should not be replaced. Participants who receive less than 90% of the total MK-1308 (or pembrolizumab) infusion in Cycle 1 (eg, if the infusion had to be discontinued due to an infusion reaction) and did not experience a DLT may be replaced (not applicable for Arm I). See Section 10.5.1 for description of safety analysis population.

If a participant experiences a DLT, trial treatment should be discontinued. However, if the participant is deriving clinical benefit from the trial treatment, the participant may be allowed to continue after discussion between the Sponsor and the Investigator.

7. Treatments

Study treatment is defined as any investigational treatment(s), marketed product(s), placebo, or medical device(s) intended to be administered to a study participant according to the study protocol.

Clinical supplies [study treatment(s) provided by the Sponsor] will be packaged to support enrollment and replacement participants as required. When a replacement participant is required, the Sponsor or designee needs to be contacted prior to dosing the replacement supplies. Clinical supplies will be affixed with a clinical label in accordance with regulatory requirements.

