
If the toxicities do resolve and conditions are aligned with what is defined in the Dose Modification and Toxicity Management Guidelines for irAEs, pembrolizumab monotherapy, coformulations, or IO combinations may be restarted at the discretion of the investigator.

Dose Modification and Toxicity Management Guidelines for irAEs associated with pembrolizumab monotherapy, coformulations, or IO combinations are provided in Table 5.

See Section 7.7.1 for supportive care guidelines, including use of corticosteroids.

Table 5Dose Modification and Toxicity Management Guidelines for Immune-related Adverse Events Associated withPembrolizumab Monotherapy, Coformulations or IO Combinations

General instructions:

- 1. Severe and life-threatening irAEs should be treated with IV corticosteroids followed by oral steroids. Other immunosuppressive treatment should begin if the irAEs are not controlled by corticosteroids.
- 2. Pembrolizumab monotherapy, coformulations or IO combinations must be permanently discontinued if the irAE does not resolve or the corticosteroid dose is not ≤10 mg/day within 12 weeks of the last treatment.
- 3. The corticosteroid taper should begin when the irAE is \leq Grade 1 and continue at least 4 weeks.
- 4. If pembrolizumab monotherapy, coformulations or IO combinations have been withheld, treatment may resume after the irAE decreased to ≤ Grade 1 after corticosteroid taper.

irAEs	Toxicity Grade (CTCAEv4.0)	Action With Pembrolizumab Monotherapy, Coformulations or IO Combinations	Corticosteroid and/or Other Therapies	Monitoring and Follow-up
Pneumonitis	Grade 2	Withhold	• Administer corticosteroids (initial dose of 1-2 mg/kg prednisone or equivalent)	 Monitor participants for signs and symptoms of pneumonitis Evaluate participants with suspected pneumonitis with
	Recurrent Grade 2 or Grade 3 or 4	Permanently discontinue	followed by taper	radiographic imaging and initiate corticosteroid treatment
				Add prophylactic antibiotics for opportunistic infections
Diarrhea / Colitis	Grade 2 or 3	Withhold	• Administer corticosteroids (initial dose of 1-2 mg/kg prednisone or equivalent) followed by taper	• Monitor participants for signs and symptoms of enterocolitis (ie, diarrhea, abdominal pain, blood or mucus in stool with or without fever) and of bowel perforation (ie, peritoneal signs and ileus)

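### Item 3 of the DLT definition exempts a Grade 3 diarrhea treated with systemic corticosteroids alone, so the Arm I DLT count can be understated

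*Combined protocol and SAP*

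**What the plan says.** **Definition (Section 7.1.1).** Item 3 makes a related non-hematologic event of Grade 3 or worse a DLT, with exceptions. One is "Grade 3 diarrhea, nausea, or vomiting without use of anti-emetics or anti-diarrheals per standard of care". The next is "Grade 3 rash without use of corticosteroids or anti-inflammatory agents per standard of care". Corticosteroids are named for rash and not for diarrhea. Item 6 adds dose delays: one clause for Dose Escalation and one reading "Prolonged delay (>2 weeks) in initiating Cycle 2 in Dose Confirmation due to treatment-related toxicity". The window itself reaches further, covering "the first 1 cycle for dose confirmation, efficacy expansion, and coformulation (Arm I only").

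**Management (Section 7.2.1, Table 5).** For Grade 2 or 3 diarrhea/colitis the action is to withhold and the drug instruction is "Administer corticosteroids (initial dose of 1-2 mg/kg prednisone or equivalent) followed by taper". Recurrent Grade 3 or any Grade 4 requires permanent discontinuation. The general instructions start the taper once the event is at or below "Grade 1 and continue at least 4 weeks". After resolution, treatment "may be restarted at the discretion of the investigator".

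**Consequence for the participant (Section 6.5).** "If a participant experiences a DLT, trial treatment should be discontinued", unless the Sponsor and investigator agree to continue because of clinical benefit.

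**Use of the count in Arm I.** Number of participants with a DLT is a primary endpoint (Section 4). The Sponsor reviews it once at least 10 participants have finished the window, without pausing enrollment (Section 5.1.4), and DLTs are listed and summarized by arm (Section 10.6.2). Section 5.1.4 and its Table 1 also give a tolerability rule for MK-1308A: at most 1 DLT in 3, or 2 in 6, per sub-cohort.

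**The concern.** The classification runs in the wrong order. A Grade 3 diarrhea controlled with an anti-diarrheal is a DLT and by default ends treatment. The same grade of event needing 1-2 mg/kg of prednisone, with no anti-diarrheal, is exempt and may be rechallenged at the investigator's discretion. A site that follows the drug instruction in Table 5 and adds nothing to it produces the exempt case.

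Two things are at stake: a possible undercount on an Arm I primary endpoint, and the loss of the Section 6.5 default for the participant concerned.

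**Working it through.** The plan states no figure on this point, so the check is a walk through the definition followed by simple arithmetic.

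**1. The case.** Arm I, Cycle 1, a first Grade 3 diarrhea, related, withheld and treated with corticosteroids only, recorded as diarrhea, treatment not discontinued in the window.

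| Item in 7.1.1 | Applies? | Reason |
|---|---|---|
| 1 | No | Grade 4 only |
| 2 | No | hematologic |
| 3 | Exempt | no anti-emetic or anti-diarrheal used |
| 4 | No | laboratory values |
| 5 | No | febrile neutropenia |
| 6 | No | coformulation phase not named |
| 7 | No | Table 5 withholds for a first Grade 3 event |
| 8 | No | Grade 5 only |

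Result: not a DLT. Changing one fact reverses it: an anti-diarrheal or anti-emetic is given; the event is recorded as colitis (Appendix 4 asks for the diagnosis rather than the symptom once one is established); treatment is discontinued in the window (item 7); the event reaches Grade 4 (item 1); or Grade 3 recurs in the window (Table 5 then requires discontinuation, hence item 7).

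**2. What item 6 would catch.** Let the taper start on Day T and last the minimum 28 days. The earliest restart is Day T + 28.
- Dose confirmation (21-day cycle, Cycle 2 due Day 22): delay = T + 28 − 22 = T + 6 days. This exceeds 14 when T ≥ 9.
- Arm I (42-day cycle, Cycle 2 due Day 43), if it were named: delay = T + 28 − 43 = T − 15 days. T = 29 gives 14, which is not more than 2 weeks; T = 30 gives 15.

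In dose confirmation, item 6 thus recovers most such events. In Arm I it recovers none as written, and would recover only tapers starting on Day 30 or later if extended.

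**3. Size per uncounted event.** 1/10 = 10 points; 1/20 = 5 points. Clopper-Pearson 95% intervals, for scale only (the SAP specifies this method for ORR and plans only listing and summary for DLTs):
- 1/10: 0.3-44.5%, reported as 0/10: 0-30.8%
- 1/20: 0.1-24.9%, reported as 0/20: 0-16.8%

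**4. Table 1, if it governs Arm I.** One uncounted event turns 2/3 into 1/3, or 3/6 into 2/6; each moves the call from de-escalate to stay. Suppose one exempt event is present and the other participants have DLTs independently at rate p. The call changes only if exactly one of the other two, or two of the other five, have a DLT.
- n = 3: 2p(1 − p). At p = 0.10: 2 × 0.10 × 0.90 = 0.18. At p = 0.25: 2 × 0.25 × 0.75 = 0.375.
- n = 6: 10p²(1 − p)³. At p = 0.10: 10 × 0.01 × 0.729 = 0.073. At p = 0.25: 10 × 0.0625 × 0.4219 = 0.264.

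The two values of p are the upper expected DLT rate and the one-fourth ceiling that Section 5.1 gives for the combination; applying them to Arm I is an assumption. These probabilities are conditional on an exempt event occurring, and its frequency is not given.

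**The case against.** **Narrowness.** Several conditions must hold together, and some pull against each other. Steroid-only treatment implies that the event was judged immune-related. For Grade 2 or worse diarrhea with suspected colitis, Table 5 advises considering gastrointestinal consultation and endoscopy, which may lead to a colitis entry and hence a DLT. The only related rate in the documents is 16.4% for diarrhea in the earlier phases (Section 5.5.3.1), about 3 in 20, not restricted to severe or first-cycle events and including higher doses. The relevant subset would be much smaller. This stands, and limits the size of the point.

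**Reading.** One could argue that a corticosteroid is the standard-of-care anti-diarrheal for immune-mediated diarrhea. Naming corticosteroids separately in the adjacent rash exception weighs against this, and a primary endpoint should not depend on how a site resolves it.

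**Existing safeguards.** Safety data are discussed at regular teleconferences (Section 9.1.8.2), unacceptable AEs require discontinuation (Section 8.1), and the event stays in the AE counts, also a primary endpoint. These protect participants and reporting in general but do not correct the DLT count.

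**Timing.** Arm I was added in March 2020 and this version is dated December 2022. Enrollment status is not stated, so rewording may come too late. The tabulation would still be useful.

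**Conclusion.** The gap is real on the wording, and minor. It rests on a literal reading of item 3 and on the conditions listed in the walk-through. Per event it costs 10 points at 10 participants or 5 at 20, and it removes the default stop in Section 6.5. No frequency can be attached to it from the documents.

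Three stronger inferences are not supported.
- A reader might infer that an Arm I dose decision is compromised. The review at 10 participants has no stated DLT threshold, and the one-fourth rule in Section 5.1 does not list Arm I. Table 1 could be affected, but its reach is unclear: it refers to sub-cohorts that are nowhere described and follows the Arm K text, although Arm I is the only coformulation arm with a DLT window. For the same reason it would be wrong to say that Arm I has no DLT threshold at all.
- A reader might infer that the Arm F clearance is in doubt. Section 5.1.3 records that its DLT period ended without toxicity concerns, and nothing indicates that an exempt event occurred there.
- A reader might treat the omission from item 6 as the main defect. The arithmetic shows that it is a secondary one.

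**What to change.** 1. **Participants already assessed:** tabulate DLTs in Arm I and in the Arm F DLT subset twice, with and without Grade 3 diarrhea treated with systemic corticosteroids. AE and concomitant-medication records already hold the data (Section 9.1.5.2), so the cost is one table.
2. **If the definition is still in use:** reword item 3 so that the diarrhea exception does not apply when systemic corticosteroids or other immunosuppressants are given, in line with the rash exception. This is one clause, but it alters a primary endpoint and should go through a protocol amendment, consistent with the opening of Section 10.
3. **As a minor supplement:** add Cycle 2 in Arm I to item 6. Alone it would not close the gap.

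The downsides are a possibly slightly higher DLT count and a small departure from the definition used in earlier phases. The second matters because Section 3.2.1.2 plans to compare coformulation safety with the co-administered products; presenting both arms under both definitions deals with it.

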• To determine the safety and tolerability of MK-1308A (Coformulation phase)	 Number of participants with ≥1 AE Number of participants discontinuing study treatment due to an AE Number of participants with ≥1 DLT (Arms I)
• To evaluate ORR as assessed by BICR per RECIST 1.1 in the efficacy expansion phase (Arms F and G). RECIST 1.1 is adjusted to follow a maximum of 10 target lesions and a maximum of 5 target lesions per organ (see Section 5.4.1.1)	• Objective Response: CR or PR
Secondary	
• To characterize the PK profiles and incidence of ADA, as appropriate, of pembrolizumab, of MK-1308 as monotherapy, and of MK-1308 when used in combination and in coformulation with pembrolizumab in the dose escalation phase as well as in Arms A, B, C, D, E, F, G, and I.	 Pharmacokinetic parameters including AUC, C_{min}, C_{max} Anti-drug antibody levels
• To characterize PK profiles and incidence of ADA of both MK-1308 and pembrolizumab in Chinese participants in Arm K when the study drugs are administered as a coformulated product (MK-1308A).	
• To evaluate ORR as assessed by investigator per RECIST 1.1 in the dose escalation phase, the dose confirmation phase, and in Arms I and K in the coformulation phase	• Objective response: CR or PR

Objective	Endpoint
• To evaluate DOR per RECIST 1.1 as assessed by BICR in the efficacy expansion phase (Arms F and G).	• DOR: The time from first documented evidence of CR or PR until disease progression or death due to any cause, whichever occurs first (for responders only)

Tertiary/Exploratory

5. Study Design

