5.1.4 Coformulation Phase for MK-1308A (Arms I and K)

The purpose of the coformulation phase is to evaluate safety, PK, and efficacy for MK-1308A, a coformulation of 25 mg MK-1308 and 400 mg pembrolizumab, 17.5-mL fill in a 20-mL vial. The coformulation PK data will be compared to the data generated in the efficacy expansion phase when these drug products were individually co-administered at the same dose level and schedule. Arm I is applicable only to sites in Israel, New Zealand, and Australia. Arm K is applicable only to sites in mainland China.

Arm I (n= up to 20) will enroll participants with advanced/metastatic solid tumors. Participants will receive MK-1308A on a Q6W schedule starting on Cycle 1, Day 1 for up to 18 cycles (~ 24 months).

Arm K (n= up to 20) will enroll participants who reside in China with advanced solid tumors. On Cycle 1, Day 1 and for all subsequent cycles, participants will receive MK-1308A on a Q6W schedule continuously for up to 18 cycles (up to 24 months).

Data from Arm K will be used to demonstrate acceptable safety and PK of MK-1308A in Chinese participants and will inform the use of MK-1308A in China in future studies,

independent of tumor type. Chinese participants who reside in China will only enroll in Arm K.

MK-1308A may be considered as tolerant if one or less participant of the first 3 experience a DLT, or if 2 or less participants of the first 6 experience a DLT (1/3 or $\leq 2/6$) for each sub-cohort (Table 1).

Number of Toxicities		f Participants Treated Current Dose
	n=3	n=6
0	S	S
1	S	S
2	DU	S
3	DU	DU
4		DU
5		DU
6		DU
S=stay at the same dose; DU=De-e Modified mTPI table based on targ		

Table 1Toxicity Assessment

Treatment Allocation

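### Arm I's primary DLT count leaves out a Grade 2 toxicity from Cycle 1 that delays Cycle 2 past Day 57 or ends MK-1308A after Day 42, because the delay criterion does not name Arm I

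*Combined protocol and SAP*

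**What the plan says.** Section 4 lists as a primary endpoint of the coformulation phase "Number of participants with ≥1 DLT (Arms I", and Section 10.4.2 names the DLT count as the primary safety endpoint. Section 7.1.1 sets the DLT window as "the first 1 cycle for dose confirmation, efficacy expansion, and coformulation (Arm I only". Section 5.1 gives its length for Arm I as 6 weeks.

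Two of the eight criteria do not depend on grade:

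- Criterion 6 covers late starts of Cycle 2 or 3 in dose escalation, and then "Prolonged delay (>2 weeks) in initiating Cycle 2 in Dose Confirmation due to treatment-related toxicity". It names neither Arm I nor Arm F.
- Criterion 7 reads "Any treatment-related toxicity that causes the participant to discontinue treatment during the DLT observation period".

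Table 5 (Section 7.2.1) tells sites to withhold, not stop, for Grade 2 pneumonitis, colitis, hepatic and renal events. The steroid taper begins once the event is at or below "Grade 1 and continue at least 4 weeks", and "treatment may resume after the irAE decreased to ≤ Grade 1 after corticosteroid taper". Table 4, footnote d, adds for toxicity ascribed to the coformulation: "participants may be re-initiated with pembrolizumab monotherapy at either 200 mg Q3W or 400 mg Q6W, after communication and agreement with the Sponsor".

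Section 5.1.4 plans a sponsor review of DLTs, meant to confirm the safety of Arm I, once at least 10 participants have completed the DLT period. Enrollment is not paused for it.

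**The concern.** The window sentence was written to include Arm I, but the delay criterion was not. Arm I is dosed once every 42 days, so the next dose falls due just after the window has closed. Whether a participant can go on with MK-1308A is often first tested at that dose. A Grade 2 toxicity that keeps the participant from an on-time second dose is therefore likely to be resolved, or to end MK-1308A, outside the window.

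Sections 5.1 and 10.5.1 treat a participant who finishes the window without a DLT as evaluable. Such a participant is not set aside but counted as DLT-free. What is at stake is a primary endpoint and the review of 10 or more participants that rests on it.

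**Working it through.** The plan states no figure that depends on this point, so there is none to reproduce. The check sets the criteria against the calendar.

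**Step 1. Which criteria can a Grade 2 event meet in Arm I?**

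| Criterion (7.1.1) | What it needs | Grade 2 event held at Cycle 2 |
|---|---|---|
| 1 | Grade 4, non-hematologic | no |
| 2 | Grade 4 hematologic, or specified Grade 3/4 thrombocytopenia | no |
| 3 | Grade 3 or worse, non-hematologic | no |
| 4 | Grade 3 or 4 laboratory value | no |
| 5 | Grade 3 or 4 febrile neutropenia | no |
| 6 | Late cycle in dose escalation or dose confirmation | no: wrong phase |
| 7 | Treatment stopped in the DLT period | only if stopped by Day 42 |
| 8 | Grade 5 | no |

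**Step 2. The Arm I calendar (first dose = Day 1).**

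- Window: 6 × 7 = Day 42.
- Cycle 2 due: 1 + 42 = Day 43.
- More than 2 weeks late: after 43 + 14 = Day 57.
- Forced permanent stop under Table 5 (event unresolved, or steroids still above 10 mg/day, 12 weeks after the last treatment): 1 + 84 = Day 85.
- A taper that starts on day s ends no earlier than s + 28. This passes Day 57 when s is 30 or more.

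Delay case: Grade 2 colitis on Day 25, Grade 1 or lower on Day 32. The taper ends on Day 32 + 28 = 60 at the earliest, so Cycle 2 is 60 − 43 = 17 days late. No criterion is met.

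Stop case: the same event, but on Day 60 the investigator and sponsor agree on pembrolizumab alone. MK-1308A has ended after one dose. The decision came after Day 42, so again no criterion is met.

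Section 9.1.8.1.2 lets Cycle 2 be given 3 days early, on Day 40. A stop decided at such a visit would be inside the window and would count under criterion 7.

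**Step 3. How criterion 6 works where it applies.**

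- Dose escalation also has a 6-week window. Cycle 3 is due on Day 1 + 2 × 21 = 43, and a toxicity delay past Day 57 is a DLT. The calendar is the same as in Arm I.
- In dose confirmation the window ends on Day 21 and Cycle 2 is due on Day 22. The criterion is met after 22 + 14 = Day 36.

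In both phases criterion 6 deliberately reaches past the window. No visible text explains why it should not do so in Arm I.

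**Step 4. How often.** The documents give no rate. The nearest figure is in Section 3.2.1.2: 12 of 179 participants in Arms A, B, C and E (12/179 = 6.7%) stopped the combination for toxicity and then started pembrolizumab alone. It is only a reference point. It covers any grade and any cycle and includes higher MK-1308 doses, but it does not include delays followed by a restart. With an assumed rate r, the chance of at least one uncounted case among n participants is 1 − (1 − r)^n:

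| r (assumed) | n = 10 (review) | n = 20 (full arm) |
|---|---|---|
| 2% | 0.183 | 0.332 |
| 5% | 0.401 | 0.642 |
| 12/179 = 6.7% | 0.500 | 0.750 |

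**The case against.** Several arguments limit the point, and most of them stand.

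- **Arm B.** A reader might infer that Arm I's DLT definition is narrower overall than that of Arm B, which has the same MK-1308 dose and interval. The documents do not support this. Arm B's window is 3 weeks. Colitis on Day 25 would not be a DLT there either, and Arm I counts Grade 3 events on Days 22 to 42 that Arm B does not. The definitions differ in both directions.
- **The 2-in-6 rule.** A reader might also infer that missed cases would change the rule in Section 5.1.4, under which "MK-1308A may be considered as tolerant if one or less participant of the first 3 experience a DLT, or if 2 or less participants" out of six do. That rule is stated for each sub-cohort, and no sub-cohorts of Arm I are described. The Arm I review at 10 or more participants is a separate step with no numeric threshold.
- **Criterion 7.** It covers any grade and does catch stops within the 6 weeks, for example Grade 2 myocarditis, which Table 5 makes a permanent stop. One could stretch it to any Cycle 1 toxicity that later ends treatment. That reading is weak: the lead-in to the list already limits toxicities to the window, and criterion 6 exists to catch late starts.
- **Other counts.** Number discontinuing due to an AE is also primary, and the natural reading includes participants who dropped MK-1308A for toxicity. They do not vanish from the report. A delay followed by a restart, however, appears only as an AE.
- **Low consequence.** The dose was chosen from 215 participants (Section 5.5.3.1), the first 6 in Arm F raised no toxicity concerns (Section 5.1.3), and all AEs are reviewed clinically. This lowers the stakes but does not close the gap in a primary endpoint.
- **Side effect of a remedy.** Section 6.5 makes discontinuation the default after a DLT, whereas Table 5 lets a resolved Grade 2 event resume. Simply widening criterion 6 would set the two against each other. This is correct, and the change has to deal with it.

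**Conclusion.** The gap is real and follows from the text alone. In Arm I, a Grade 2 toxicity with onset in Cycle 1 that delays Cycle 2 past Day 57, or leads after Day 42 to MK-1308A being dropped, meets none of criteria 1 to 8. It is left out of the primary DLT count and of the review at 10 or more participants. The direction is known: the count can only come out too favourable. The size is not known, because the documents give no rate. Under an assumed 2% to 6.7%, at least one such case would be expected with a chance of 18% to 50% in 10 participants and 33% to 75% in 20.

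The conclusion does not extend to every Grade 2 stop, to an overall comparison with Arm B, or to any effect on the 2-in-6 rule. The change is worth making because it is small and the endpoint is primary. The gap does not undermine the rest of the safety assessment.

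**What to change.** Three changes:

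1. **Section 7.1.1, criterion 6.** Add: *In Arm I, and in the DLT-evaluable participants of Arm F (for MK-1308 plus pembrolizumab), a Cycle 2 that starts more than 2 weeks late or is not given, because of treatment-related toxicity with onset in Cycle 1. This applies also if pembrolizumab alone is given afterwards.*
2. **Section 6.5.** Add: *A DLT that is met only through this delay does not by itself require discontinuation when the Table 5 conditions for resuming are fulfilled.*
3. **Participants already treated in Arms F and I.** Report the DLT count under the amended criteria beside the count under the current criteria. Arm F's review of the first 6 is complete, so there this is a re-count only.

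Cost: two added sentences and one extra tabulation, from dosing dates and AE records that are already collected. No participants or visits are added. A participant with a late Cycle 2 has a final DLT status at about Day 57 instead of Day 42. Because Arm I enrollment is not paused for the DLT review, recruitment does not wait. The DLT count may come out slightly less favourable.
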